#### **Prior/Concomitant Therapy**

27 Participants currently receiving background therapy that is not approved by regulatory authorities in the country of study for COPD are not eligible for the study.

AstraZeneca

- 28 History of treatment with cardiotoxic medications (eg, as part of cancer therapy) including thiazolidinediones.
- 29 Major surgery within 8 weeks prior to screening or planned inpatient surgery or hospitalization during the study period. Elective hospitalizations that cannot be delayed until after the end of the study need to be discussed with the sponsor's medical monitor.
- 30 Treatment with broad spectrum antibiotic within 4 weeks prior to randomization (Day 1).
- 31 Donation of blood or blood products in excess of 500 mL within 3 months prior to screening.
- 32 History of allogeneic bone marrow transplant.
- 33 Treatment with allergy immunotherapy within 90 days prior to SV1.
- 34 Receiving any of the prohibited concomitant medications as specified in the CSP:
  - (a) Acute systemic (oral or injectable) corticosteroids within 4 weeks of SV1
  - (b) Any other immunosuppressive therapy (including methotrexate, cyclosporine or maintenance systemic steroid treatment) wit in 3 donths of randomization.
  - (c) Immunoglobulin or blood products within weeks of SV1.
  - (d) Live or attenuated vaccines within 4 week of SV1. (Note: Vaccines with adenoviral vectors that are unable to replicate, or ChAdOx1, are not considered live or attenuated).
  - (e) Interferon gamma within 3 mon 's of andomization.
  - (f) Investigational products with. 4 months or 5 half-lives of randomization, whichever is longer.
  - (g) Marketed biologics within months or 5 half-lives of randomization, whichever is longer.
  - (h) Any add-on therapy for OPD including theophylline. Chronic macrolide or other antibiotic therapy is an swed provided the participant has been on a stable dose/regimen for > 3 months prior to enrolment and has had at least one COPD exacerbation while on stable therapy.
  - (i) PDE4 inhibitors (e.g. roflumilast, Daxas®, Daliresp®) commenced within 3 months of SV1. PDE4 inhibitors are allowed provided the participant has been on a stable dose/regimen for ≥ 3 months prior to enrolment and has had at least one COPD exacerbation while on stable therapy.
  - (j) Vaccination against COVID-19 (either first or subsequent dose) within 30 days prior to randomization.
  - (k) Any immunotherapy within 3 months of randomization.
  - (l) Antitussive and mucolytic medications commenced within 4 weeks prior to SV1. Antitussive and mucolytic medications are allowed provided the participant has been on a stable therapy/regimen for greater than 4 weeks.

AstraZeneca

35 Participation in, or scheduled for, an intensive COPD rehabilitation program at any time during the intervention period (note: participants are permitted to be in the maintenance phase of a rehabilitation program).

# **Prior/Concurrent Clinical Study Experience**

36 Concurrent enrolment in another clinical study involving an investigational treatment.

#### **Exclusion Criteria for Optional Genetic Sample Only**

37 Non-leukocyte depleted whole blood transfusion within 120 days of optional genetic sample collection.

#### **Other Exclusions**

- Participant is an investigator, sub-investigator, such value coordinator, or employee of the participating site or Sponsor, or is a first-degree relation of the aforementioned.
- 39 Inability to perform technically acceptable spin meuy.
- 40 Pregnancy or intention to become pregnant during the study, breastfeeding, or unwillingness to use a highly effective rethed of contraception throughout the study in female participants of childbearing potential.
- 41 This criterion has been removed.

# 5.3 Lifestyle Considerations

Participants must abstain from donating blood and plasma from the time of informed consent, and for 16 weeks (5 half-lives) after last dose of study intervention.

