Injection-site reactions	This is based on the SC route of administration and the nature of MEDI3506 as an exogenous protein substance.	
 
Instructions on injection technique including rotation of injection sites.
 
Routine monitoring for injection site assessments will be undertaken at each visit.
 
Routine blinded review of the safety data for appearance of injection site reactions
 
See IB Section 5.5.3.1
 
									

Table 4 Risk Assessment

Potential Risk of Clinical Significance	Summary of Data/Rationale for Risk	Mitigation Strategy
Serious hypersensitivity (including Type 1 to 4 hypersensitivity reactions) and Immune Complex Disease	As mAbs are foreign proteins they have the potential to provoke hypersensitivity reactions. Based on a potential risk known to be associated with foreign proteins, occurrence of ADAs could result in immune complex disease.	
 
Exclusion Criteria 8, 19, and 32
 
Routine blinded review of the safety data, including anaphylactic symptoms
 
Required monitoring of participants for a minimum of 1 to 2 hours after study intervention administration Sites should be trained to recognise, and equipped to manage, anaphylaxis and serious allergic reactions until the participant can be transferred to a suitable facility (see Appendix I)
 
See IB Section 5.5.4.1
 

Reproductive toxicity	Consistent with ICH guidance on the timing of nonclinical studies, MEDI3506 has not been evaluated in embryo-fetal development toxicity studies	
 
Stipulation of highly effective contraceptive requirements for participants
 
Inclusion Criteria 14, 15, 16
 
See IB Section 5.5.5.1
 

CCI	Temporary, mi or discomfort (similar to drawing blood).	
 
To be performed by appropriately trained staff.
 
If deemed by the investigator to be intolerable for individual participant at SV3 (eg, due to nasal polyps), subsequent assessments may be omitted (see Table 3).
 

AstraZeneca

Table 4 Risk Assessment

Potential Risk of Clinical Significance	Summary of Data/Rationale for Risk	Mitigation Strategy

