#### Follow up Period

Follow-up visits will occur 4 and 8 weeks after EOT visit to allow for determination of immunogenicity and potential prolonged PD effects, and evaluation of safety. Participants will be discharged from follow-up 3 months after the last dose of study intervention.

The maximum amount of blood collected from each participant over the duration of the study, including any extra assessments that may be required, will not exceed 450 mL in 3 months. Repeat or unscheduled samples may be taken for safety reasons or for technical issues with the samples.

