#### 4.2.3 Rationale for Intervention Period Duration

The last dose is administered at Week 24 and the end of treatment is 4 weeks later (Week 28).

Based on available data, the improvement in FEV1 assumed in the sample size determination (Section 9.2) is expected to be achieved by Week 12. However, improvement in FEV1 is considered important but not sufficient to meet the unmet medical need in COPD. To enable evaluation of the secondary endpoint of COPDCompEx, the treatment is continued after collection of primary endpoint data, to collect further events.

AstraZeneca

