## **Sex/Reproduction:**

- 14 Female participants of childbearing potential, must have negative pregnancy tests at screening SV1 (serum pregnancy test), and then subsequently at SV2 (urine pregnancy test, only if a CT scan is performed) and pre-dose of study intervention at SV3 (Day 1; urine pregnancy test).
- 15 Female participants of childbearing potential who are sexually active with a male partner must agree to use a highly effective method of contraception from screening until the end of the follow-up period at SV14 of the study. See Appendix F for definitions of childbearing potential and highly effective methods of contraception. In countries where spermicide is available, it is strongly recommended for the male partner of a female participant of childbearing potential to also use male condom plus spermicide throughout

AstraZeneca

this period.

In countries where spermicide is not available, it is strongly recommended for the male partner of a female participant of childbearing potential to also use male condom throughout this period.

Note there are no contraception requirements for female participants who are not of childbearing potential. However, all female participants should refrain from egg cell donation and breastfeeding throughout the study.

In countries where spermicide is available, male participants who are sexually active with a female partner of childbearing potential must agree to use a male condom with spermicide and another highly effective method of contraception during the intervention and follow-up periods from Day 1 through to SV14 of the study.

In countries where spermicide is not available, male participants who are sexually active with a female partner of childbearing potential must agree to use a male condom and another highly effective method of contraceptio. during the intervention and follow-up periods from Day 1 through to SV14 of the study.

See Appendix F for definitions of childbearing potential and highly effective methods of contraception. Male participants should also retrain from biologically fathering a child or donating sperm during the same period.

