## 8.3.10.2 Paternal Exposure

Male participants should refrain from fathering a c'ild or donating sperm during the study and for 12 weeks after the last administration of study intervention.

Pregnancy of the participant's partners is not considered to be an AE. However, the outcome of all pregnancies (spontaneous miscar has cleetive termination, ectopic pregnancy, normal birth or congenital anomaly), occurring from the date of the first dose until the end of follow-up should, if possible, be followed up and documented in the Pregnancy Report Form. Consent from the partner must be obtained before the Pregnancy Report Form is completed.

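### Two post-dose intervals are used without a stated reason: blood donation is barred for 16 weeks (5 half-lives), but after a Week 24 dose the reproductive precautions end at 12 weeks

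*Protocol*

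**What the plan says.** - **Blood and plasma.** Protocol Section 5.3 forbids donation from informed consent "and for 16 weeks (5 half-lives) after last dose of study intervention".
- **Women of childbearing potential.** Inclusion criterion 15 (Section 5.1) states that those having sex with men "must agree to use a highly effective method of contraception from screening until the end of the follow-up period at SV14 of the study".
- **Men.** Inclusion criterion 16 requires contraception, and bars fathering a child or donating sperm, from Day 1 through SV14. Section 8.3.10.2 sets the fathering and sperm limit as the study period and "for 12 weeks after the last administration of study intervention".
- **Pregnancy reporting.** Section 8.3.10 asks for all pregnancies and outcomes, except those discovered before any dose, and gives no end date. Section 8.3.10.1 ties prompt notification to pregnancies during the study. Section 8.3.10.2 follows partner pregnancies that occur between the first dose and the end of follow-up.
- **Timing.** Section 4.2.3 places the last dose at Week 24 and the end of treatment at Week 28. Under Follow up Period in Section 4.1, "Follow-up visits will occur 4 and 8 weeks after EOT visit", and participants are "discharged from follow-up 3 months after the last dose of study intervention". Table 3 puts SV14 at Week 36.
- **Risk.** Table 4 in Section 2.3.1 lists reproductive toxicity as a potential risk and states that "MEDI3506 has not been evaluated in embryo-fetal development toxicity studies". It names contraception as the mitigation and refers to the Investigator's Brochure.

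**The concern.** The protocol gives one explicit link between calendar time and elimination of the drug: 16 weeks equals 5 half-lives. It applies that link to blood donation. The precautions against fetal exposure stop 4 weeks sooner for anyone who takes the seventh dose, although contraception is the listed mitigation for a risk with no embryo-fetal data. Five half-lives also appears elsewhere in the protocol as a clearance yardstick: exclusion criteria 34(f) and 34(g) and Section 6.5.5 use it, as the alternative to 4 months, for earlier investigational products and biologics.

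At stake is a participant-safety rule. Either the precaution period is shorter than the sponsor's own view of elimination would suggest, or the half-life statement in Section 5.3 is not the figure on which the other limits were set. A participant leaving at SV14 would still be barred from giving blood on half-life grounds while the contraception and sperm-donation limits had ended. The trial's sample size, endpoints and analyses are not touched.

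**Working it through.** **Inputs**
- Donation limit: 16 weeks = 112 days, equated with 5 half-lives (Section 5.3).
- Last planned dose: Week 24, Day 169 (Section 4.2.3; Table 3).
- SV14: Week 36, Day 253, with a window of ±3 days for SV5 to SV14 (Table 3).
- Fathering and sperm limit: 12 weeks = 84 days after the last dose (Section 8.3.10.2).

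**Step 1: implied half-life.** 112 / 5 = 22.4 days, or 3.2 weeks. Reproducing the plan's figure, 5 × 22.4 = 112 days = 16 weeks. This is true by construction, because the protocol states no half-life independently.

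**Step 2: last dose to SV14.** 253 − 169 = 84 days = 12 weeks, the same as the explicit limit for men. With the visit windows at both ends, the range is 250 − 172 = 78 days to 256 − 166 = 90 days.

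**Step 3: half-lives covered and fraction remaining,** with half-lives = days / 22.4 and fraction = 2^(−days/22.4), assuming first-order decline.

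| Days after last dose | Half-lives | Drug remaining |
|---|---|---|
| 78 | 3.48 | 8.9% |
| 84 (12 weeks) | 3.75 | 7.4% |
| 90 | 4.02 | 6.2% |
| 112 (16 weeks) | 5.00 | 3.1% |

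The difference is 28 days, or 28 / 22.4 = 1.25 half-lives. The residual at 12 weeks is 2^1.25 = 2.4 times that at 16 weeks.

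**Step 4: who is affected.** Section 7.1 keeps participants who stop treatment in the study through all remaining visits, so the interval to SV14 depends on the last dose received.

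| Last dose | Weeks to SV14 | Half-lives |
|---|---|---|
| Week 24 | 12 | 3.75 |
| Week 20 | 16 | 5.00 |
| Week 16 | 20 | 6.25 |

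Only the Week 24 row falls below 5.

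**Step 5: sensitivity to the half-life.** Twelve weeks would reach 5 half-lives only if the half-life were at most 84 / 5 = 16.8 days. At 16.8 days, 16 weeks would be 112 / 16.8 = 6.7 half-lives, and the statement in Section 5.3 would be wrong. Over an assumed range of 14 to 24 days, 12 weeks covers 6.0 to 3.5 half-lives. At an assumed 21 days it covers 4.0. No single half-life makes both periods equal to 5 half-lives.

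**The case against.** The strongest reply is that nothing conflicts. One rule protects recipients of donated blood; the others concern conception and gamete donation. A participant can obey all of them, and no section says contraception must last 5 half-lives. The reproductive limits also agree with one another: SV14, 12 weeks, the end of follow-up, and discharge at 3 months. This stands, and it rules out calling the limits contradictory, as a reader might.

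A reader might also infer that pregnancy reporting stops at 12 weeks, so that a conception between 12 and 16 weeks would be neither prevented nor captured. The text does not support that. Section 8.3.10 sets no end date, and Section 8.3.10.1 has no 12-week limit. It treats congenital anomalies and spontaneous miscarriages as serious adverse events, and Section 8.3.1 requires a suspected-related serious event in a treated participant to be reported even after the study ends. Only the partner-pregnancy window closes with follow-up.

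A third temptation is to convert the percentages into serum concentrations from the predicted steady-state average of 21 µg/mL in Section 4.3. That is an average, not the level at the last dose, and the documents give no concentration threshold for fetal concern. Drug also remains at 16 weeks, so that point is not a boundary between exposed and unexposed.

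Two further limits stand. The half-life comes from a single parenthesis that may be rounded, and Table 4 refers to an Investigator's Brochure that is not available here, so the missing rationale is shown only for the protocol text. With participants aged 40 to 80, few women are likely to be of childbearing potential, although criterion 16 also covers men with such partners.

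None of this explains the 4-week difference.

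**Conclusion.** The point holds as an unexplained inconsistency in how post-dose exposure is treated. For participants who receive the Week 24 dose, contraception, the limit on fathering and sperm donation, and the partner-pregnancy window all end 12 weeks later. On the protocol's own figure that is 3.75 half-lives (3.5 to 4.0 with visit windows), against 5 for blood donation: a shortfall of 4 weeks or 1.25 half-lives, with about 7.4% of drug remaining rather than 3.1%. It does not apply to those last dosed at Week 20 or earlier who stay to SV14.

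The size rests on the half-life implied by Section 5.3 and on first-order elimination. The documents do not establish that the longer period is the right one for contraception; they show only that the figures do not share a basis.

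**What to change.** Reconcile Section 5.3, inclusion criteria 15 and 16, Sections 8.3.10 to 8.3.10.2 and Table 4 so that the limits on blood donation, contraception, gamete donation and pregnancy reporting rest on one stated half-life, and correct whichever figure does not. State the half-life explicitly, and express each limit as time since the last dose received as well as by visit, so that it reads the same for completers and early stoppers. The sponsor's medical team decides the period.

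The cost is a protocol and consent wording update. If any reproductive limit ends up beyond SV14, a telephone contact after that visit may be wanted, because none is scheduled.

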#### **5.3.1** Meals and Dietary Restrictions

Participants should avoid eating a large meal for at least 2 hours prior to all scheduled lung function and AO assessments at the site.

AstraZeneca

### 5.3.2 Caffeine, Alcohol, and Tobacco

Chronic alcohol or drug abuse within 2 years is restricted prior to SV1 and throughout the conduct of the study.

Current tobacco smokers or prior tobacco smokers, with smoking history  $\geq 10$  pack-years (1 pack-year = 20 cigarettes smoked per day for 1 year) at SV1 are allowed. Never smokers are not allowed to enter the study. Any change in smoking status in 12 weeks prior to enrolment or intention to change smoking status between enrolment and end of follow-up will result in a screen failure. However, following change in smoking status, they will be eligible for re-screening. Smoking status changes during the course of the study will be captured on the eCRF but the participant will be permitted to continue in the study. See also Section 8.

The use of e-cigarettes (eg, JUUL) is allowed during the course of the study.

# 5.3.3 Activity

- Participants should avoid engaging in strenucu. exertion for at least 30 minutes prior to all scheduled lung function assessments, AO nd lood collection at the site.
- 2 Participants should avoid showers/bathir a and any activity that will cause heavy perspiration whilst wearing the cough monitor, as the cough monitor must not come into contact with water.

#### 5.4 Screen Failures

Screen failures are defined as partici, and who consent to participate in the clinical study but are not subsequently randomly assigned to study intervention. A minimal set of screen failure information is required to ensure ansparent reporting of screen failure participants to meet the Consolidated Standards of eporting Trials publishing requirements and to respond to queries from regulatory authorities. Minimal information includes demography, screen failure details, eligibility criteria, and any SAEs.

Individuals who do not meet the criteria for participation in this study (screen failure) may be rescreened, if there is reason to believe the reason for ineligibility was temporary (eg. exacerbation and/or background medication stability periods). Only one rescreening per participant is allowed in the study, when there is a reasonable expectation that the participant will become eligible for the study. Prior to rescreening, participants must be reconsented. Participants in rescreening retain their previous E-code.

Where individuals are rescreened, the results of echocardiogram and IGRA (TB test) carried out as part of the original screening process can be included as long as they are within the last 3 months and there have been no specific risks of TB infection such as foreign travel to a high

AstraZeneca

incidence area and no recent cardiac events which may affect the echocardiogram.

All other tests must

be performed as per the schedule of events (Table 2).

#### **6** STUDY INTERVENTION

Study intervention is defined as any investigational intervention(s), marketed product(s), placebo, or medical device(s) intended to be administered to a study participant according to the CSP. Study intervention in this study refers to MEDI3506 and placebo.

# 6.1 Study Intervention Administered

# **6.1.1 Study Interventions**

**Table 6 Study Interventions** 

ARM Name	MEDI3506 CCI	Placebo		
Intervention Name	MEDI3506	Placebo		
Туре	Biologic	Drug		
Dose Formulation	CCI	CCI		
Unit Dose Strength(s)	CCI	Not applicable		
Dosage Level(s)	CCI	CCI		
Route of Administration	CCI	CCI		
Use	Experimental	Placebo-comparator		
IMP and NIMP	IMP	IMP		
Sourcing	Provided centrally by the Sponsor	Provided centrally by the Sponsor		
Packaging and Labelling	CCI	CCI		

IMP = Investigational medicinal product; NIMP = Non-investigational medical product; Q4W = Every 4 weeks; SC = Subcutaneous; w/v = Weight per volume.

AstraZeneca

# 6.2 Preparation/Handling/Storage/Accountability of Interventions

- 1 The investigator or designee must confirm appropriate temperature conditions have been maintained during transit for all study intervention received and any discrepancies are reported and resolved before use of the study intervention.
- Only participants enrolled in the study may receive study intervention and only authorised site staff may supply or administer study intervention. All study intervention must be stored in a secure, environmentally controlled, and monitored (manual or automated) area in accordance with the labelled storage conditions with access limited to the investigator and authorised site staff.
- 3 MEDI3506 does not contain preservatives and, therefore, any unused portion must be discarded.

The unblinded study intervention manager will select the appropriate kits allocated by the RTSM system to prepare the participant's dose. The vi. linded study intervention manager must ensure that only the unblinded team members have access to the areas of the pharmacy where the study intervention is being stored and prepared.

# 6.2.1 Study Intervention Inspection

Each vial allocated for dose preparation shou. be inspected. MEDI3506 and placebo are supplied as a clear to opalescent sterile it, ids

If there are any defects noted with the stucy intervention, the investigator and site monitor should be notified immediately. For to the Product Complaint section in the IMP manual for further instructions.

# 6.2.2 Dose Preparation Suns

No incompatibilities betw en MEDI3506 and plastics (ie, polypropylene and polycarbonate syringes) have been observed.

MEDI3506 and placebo do not contain preservatives and any unused portion must be discarded. Preparation of study intervention is to be performed aseptically. Total in use storage time from needle puncture of the study intervention vial to start of administration should not exceed 4 hours at room temperature or 24 hours at 2 °C to 8 °C (36 °F to 46 °F). If storage time exceeds these limits, a new dose must be prepared from new vials assigned by the RTSM system.

A vial should be used only 1 time to prepare a single dose.

To prepare the participant's dose, the unblinded study intervention manager will select study intervention for administration according to the kit identification numbers assigned. A

AstraZeneca

summary of the study intervention volumes required and syringes to prepare for SC dose administration in each study intervention group is provided (Table 7).

 Table 7
 Study Intervention Dose Preparation

Contents of vial(s)	Number of kits	Volume required	Syringes to prepare	Size of syringe	Total volume of study intervention	
MEDI3506 intervention group						
MEDI3506	CCI					
Placebo intervention group						
Placebo	CCI					

The dose preparation steps are as follows:

- Prepare the assigned MEDI3506 and/or placebo vials for the particular study intervention group as per Table 7.
- Withdraw the required volume of MEDI3506 c. nacebo from each vial using a separate, appropriately sized syringe and a separa. 19 to 20-gauge 1 to 1.5 inch needle, respectively.

